**Title: Effect of Sport Education in University Required PE on Students'
Perceived Physical Literacy and Physical Activity Level**

NCT number: NCT03888885

Date: 12/9/2021

Statistical Analysis Plan

ActiLife 6 software (ActiGraph LLC), a designated software for transferring data from accelerometers to computers, was used to transfer physical activity data with a metabolic cut point of Freedson et al. (1998). IBM SPSS statistics version 22 for Windows (IBM SPSS) was used for all data analysis (Field 2009). One-way analyses of variance (ANOVAs) were used to assess differences between groups in the baseline measures of demographic information, each outcome measure, as well as the mean percentage of physical activity levels, lesson context, and teacher involvement during PE lessons. Pearson's correlation was used to compute the association between self-report and objective physical activity levels. To evaluate the effect of the different types of curriculum interventions on outcome measures, a series of repeated-measures multivariate analysis of variance (MANOVAs) were used with time (baseline, post-intervention, and follow-up) as the within-subjects factor and group (intervention group and control group) as the between-subjects factors. MANOVA analyses are the most appropriate analyses to discern differences between groups over time and to establish any potential group by time interaction effects (Tabachnick and Fidell 2014). Specifically, MANOVA is likely to prevent type I error when dependent outcomes may be correlated and thus potentially share some of the same variances. Post hoc Scheffe analyses were conducted to determine contributing factors to significant MANOVA F values. The significance level was set at 95% for all analyses.

References

Field, A. (2009). *Discovering statistics using SPSS*. London: SAGE Publications Ltd.

Freedson, P. S., Melanson, E., & Sirard, J. (1998). Calibration of the computer science and applications, inc. accelerometer. *Medicine and Science in Sports and Exercise*, 30(5), 777–781.

Tabachnick, B. G., & Fidell, L. S. (2014). *Using multivariate statistics*. Harlow: Pearson Education Limited.

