**Title: Effect of Sport Education in University Required PE on Students'
Perceived Physical Literacy and Physical Activity Level**

NCT number: NCT03888885

Date: 12/9/2021

Study Protocol

Research design

This study employed a 10-lesson cluster-randomized study design to examine the effect of sport education on domains of student PL and physical activity levels. Questionnaires, accelerometers, and video recordings of PE lessons were used to collect self-report and objective data measures.

[figure not shown]
Eligibility and randomization

Only one university in Hong Kong fully funded by the University Grants Committee and requires the completion of two semesters of PE coursework for graduation. Lecturers in the PE program are required to have a master's degree or above and have more than 5 years of teaching experience. All lecturers attended a 12-h continuous professional development workshop on sport education. Of the 25 lecturers who attended the workshop, 11 of them consented to participate in the study. The required sample size of students was calculated based on the hypothesized effect sizes and the likely rates of participants dropout for outcome measures. A total number of 2886 students were admitted to the university in the academic year, with an estimated required cluster sample size of 341 with an effect size of 0.25, α of 0.05, and a power of 0.95 (Faul et al. 2007). In anticipation of 10–20% of the dropout rate across data collection phases, this led to a required number of 8 classes for each of the sport education and traditional groups. PE classes were initially grouped by lecturers and types of sports (individual sports, team sports, and physical conditioning) and then randomly assigned to each intervention (Fig. 1) by a computer-generated sequence (GraphPad Software, Inc.) conducted by a statistician who was blind to the purposes of the study. The demographic background and corresponding courses for each of the eight lecturers are shown in Table 1. Students were eligible to participate in the study if they were aged 18 or above and indicated all negative statements in the self-screening Physical Activity Readiness Questionnaire (Thomas et al. 1992) which can uncover heart, circulatory, balance, medication, emotional, and joint problems that could make exercise difficult or dangerous for some people. Written consent for study participation was also obtained.

PE curriculum intervention

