Participants within the control group classes attended PE classes where teachers used traditional teacher-directed methods to teach the specific activities. These lessons started with a teacher-directed warm-up routine, followed by direct instruction of skills practices, and games without a consistent team and modification to meet the objective of the courses. Within the direct teaching approach, the teacher was assigned responsibility for all task presentation components of the learning tasks. No student role responsibilities or student-directed tasks were included within this approach. Students within the intact class changed teams each lesson and scores were not formally recorded for the game outcomes. Analysis with the sport education benchmark observational instrument revealed none of the instructional behaviors associated with the key features of the model.

Data collection protocol

During the first week of the semester, a baseline questionnaire was distributed by the researchers and lecturers to all participants to obtain students' self-reported information including perceived PL, physical activity levels, and perceptions of motivational climate in PE classes. Demographic information is related to participants' age, gender, ethnicity, undergraduate program and year of study, and years of sport participation. PL is both an antecedent and consequence of physical activity (Edwards et al. 2017) and represents the lived experience of the PL journey of an individual (Sum et al. 2018a). A primary outcome measure was the participants' self-reported and objective physical activity levels. As there may be an over-reporting of the self-report physical activity levels, a subsample of 64 randomly selected student participants per intervention group also collected objective physical activity levels using accelerometers. Accelerometers were worn for at least 8 h per day in seven consecutive days during the first week of the semester. During the intervention, all lessons were videotaped and coded using the System for Observing Fitness Instruction (SOFIT) which elicits percentage of PE time at different intensities of physical activity, lesson context, and teacher involvement in PE lessons. Participants recompleted the questionnaire, and the subsample wore the accelerometers during the post-intervention phase (the 10th lesson at 11th week of semester) and the follow-up phase (15th week of semester).

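### One-way ANOVA is specified for unordered baseline categories, and the baseline and SOFIT comparisons take no account of the randomised classes or lecturer/sport groupings

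*SAP*

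**What the plan says.** The SAP's single section gives one rule for group comparisons outside the main model: "One-way analyses of variance (ANOVAs) were used to assess differences between groups in the baseline measures of demographic information". The same sentence extends it to baseline values of each outcome and to the SOFIT percentages for student activity, lesson context and teacher involvement. No test for categorical data is named anywhere. No unit of analysis is stated, and there is no class, lecturer or stratum term and no ICC.

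The protocol (Data collection protocol) lists the demographic variables as "age, gender, ethnicity, undergraduate program and year of study, and years of sport participation". It also says that every lesson was videotaped and SOFIT-coded during the intervention.

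On design, the protocol (Research design) says "This study employed a 10-lesson cluster-randomized study design". Under Eligibility and randomization it says "PE classes were initially grouped by lecturers and types of sports" before allocation and gives a "required number of 8 classes for each of the sport education and traditional groups".

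**The concern.** Ethnicity and undergraduate program have no natural order. A one-way ANOVA on them compares the mean code number between arms, which depends on how someone numbered the categories. The result cannot be interpreted as evidence for or against balance.

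Separately, whole classes were allocated. If students in a class resemble each other more than students in different classes, an ANOVA on individual students overstates the information in 16 classes. The same holds for SOFIT if each of a class's ten lessons counts as an independent observation.

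The stakes differ. The baseline tests support only a statement that the arms were comparable. The SOFIT comparison is made on data collected after randomisation. It is a comparison of the two teaching approaches, and this sentence is the only analysis the SAP names explicitly for it.

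**Working it through.** **1. Code dependence (illustrative counts, not trial data).** Take 192 students per arm and four programs, with counts 60/48/44/40 against 44/60/40/48.

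- Chi-square: the expected counts are 52, 54, 42 and 44 in each arm, and the deviations are 8, 6, 2 and 4. The statistic is 2 × (64/52 + 36/54 + 4/42 + 16/44) = 4.71 on 3 df, p = 0.19.
- ANOVA with codes 1, 4, 2, 3: mean codes are 460/192 = 2.40 and 508/192 = 2.65, p = 0.035.
- ANOVA with codes 3, 4, 2, 1: mean codes are 500/192 = 2.60 in both arms, p = 1.00.
- Over all 24 numberings p runs from 0.035 to 1.00, and 4 of the 24 fall below 0.05.

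A two-category variable does not have this problem. With 90/81 against 75/96, ANOVA gives p = 0.105 under every coding tried, and chi-square gives the same to within rounding. Coding alone does not raise the false-positive rate either: with independent students and a four-category variable, simulation gave 5.5%.

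**2. Inputs for clustering.**

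- Classes: 8 per arm (Protocol, Eligibility and randomization).
- Class size: not stated. The protocol gives "an estimated required cluster sample size of 341 with an effect size of 0.25, α of 0.05, and a power of 0.95" and 10–20% dropout. If 341 is the total, 341/0.9 = 379 and 341/0.8 ≈ 427, or about 24 to 27 students per class over 16 classes. I use 24. The basis of the 341 is not fully stated and I could not reproduce it, but nothing here depends on it beyond this class size.
- Lessons: ten per season (Protocol, PE curriculum intervention).
- ICC: none given. Assumed 0.02–0.10 for baseline variables and 0.2–0.5 for lessons within a class.
- Pairing: eight lecturers and 16 classes suggest 8 lecturer/sport pairs, but the documents do not confirm this. Assumed.

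**3. Formula.** Let ρ be the ICC, m the observations per class, and s the share of the clustering common to both classes of a pair. The shared part cancels between arms. The true variance of the arm difference, relative to the variance that the naive test assumes, is approximately

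V = (1 − ρ) + m·ρ·(1 − s).

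The false-positive rate is 2 × [1 − Φ(1.96/√V)]. With s = 0, V is the usual 1 + (m − 1)ρ. Example: m = 24, ρ = 0.05, s = 0.5 gives V = 0.95 + 0.60 = 1.55 and a rate of 11.5%.

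| Comparison | ICC | none shared | half shared | 90% shared |
|---|---|---|---|---|
| Baseline, m = 24 | 0.02 | 10.5% | 7.6% | 5.3% |
| Baseline, m = 24 | 0.05 | 18.1% | 11.5% | 5.8% |
| Baseline, m = 24 | 0.10 | 28.1% | 17.6% | 6.6% |
| SOFIT, m = 10 | 0.2 | 24.2% | 14.4% | 5.0% |
| SOFIT, m = 10 | 0.5 | 40.3% | 25.8% | 5.0% |

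Simulation with 20,000 null trials per cell agrees to within about two percentage points and is mostly slightly higher. The rounded ranges from formula and simulation together are 11–28%, 7–19% and 5–7% for baseline, and 24–42%, 15–27% and 5–7% for SOFIT.

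Inflation requires m(1 − s) > 1. More than 1/24 (about 4%) of the clustering must be class-specific for students, and more than 1/10 for lessons. If all of it is shared, the naive test is conservative.

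**4. Alternatives.** In the same simulations a paired class-mean test held about 5% throughout. An unpaired 8 versus 8 class-mean test held 5% only when nothing was shared, and fell to between about 0.1% and 2.4% when 90% was shared.

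**The case against.** The strongest reply is that the baseline tests are descriptive. The SAP ties no covariate, exclusion or model choice to them, and its repeated-measures MANOVA has no covariates. That stands. A reader might infer that wrong adjustments would follow from these p-values, but the documents describe no such step.

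Three stronger readings are tempting and should be resisted:

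- **All baseline p-values depend on coding.** They do not. Age, years of sport, the scale scores and two-category gender are unaffected, and year of study has an order. Arbitrary coding also does not create excess false positives; that can come only from the ignored clustering.
- **The error rate is 11–28%, or 24–42% for SOFIT.** Those are the upper ends, with nothing shared within lecturer/sport groupings. Grouping before allocation can remove much of the effect. One might add that students choose classes by sport and so cluster by gender or experience, but the protocol does not describe how students enrol, and sorting by sport is partly what the grouping balances.
- **The SOFIT analysis certainly treats lessons as independent.** The SAP refers to mean percentages and names no unit, so class means are a possible reading. A plain one-way ANOVA on class means would still omit the grouping and could then be too conservative.

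What survives is that the rule as written is unsuitable for two variables, and that neither the unit nor the allocation structure is specified for any of these tests.

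**Conclusion.** The point holds in this limited form. For ethnicity and undergraduate program, the specified ANOVA has no meaningful interpretation; this follows directly from the text and needs no assumption about the data. For the other comparisons, p-values are probably too small if students or lessons are the unit. How much too small cannot be fixed from the documents: from close to the nominal 5% up to 28% (baseline) or 42% (SOFIT) over the assumed ICCs, depending mainly on how much clustering the lecturer/sport groupings share.

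The baseline part is minor and limited to the comparability statement. The SOFIT part matters more, because it bears on whether the teaching approaches differed in lesson activity, context and teacher behaviour. This sentence of the SAP does not govern the main outcome model, and nothing here shows a main result to be wrong.

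**What to change.** **Baseline.** Drop the significance tests. Present a table by arm with counts and percentages for gender, ethnicity, program and year of study; mean and SD for age, years of sport and the outcome scores; and standardised differences.

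**SOFIT.** State the unit of analysis. Either compare class means with the lecturer/sport grouping as a pairing or stratum term, or fit a mixed model to lesson percentages with class as a random effect and the grouping included. An unstratified 8 versus 8 comparison of class means is not a good substitute, because it becomes too conservative when the groupings share clustering.

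**Cost.** Changed SAP wording and a reanalysis of data already collected. The small downside is fewer degrees of freedom for SOFIT (8 − 1 = 7 for a paired test if there are eight pairs) and wider intervals than a lesson-level analysis would show.

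### PE classes were randomised but students are analysed: the SAP's MANOVAs have no class term, so class-specific change can push the type I error well above 5%

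*SAP*

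**What the plan says.** The protocol (Research design) states: "This study employed a 10-lesson cluster-randomized study design". Under Eligibility and randomization it adds that "PE classes were initially grouped by lecturers and types of sports" before computer-generated assignment. After the allowance for dropout, "this led to a required number of 8 classes for each of the sport education and traditional groups". The same section refers to eight lecturers.

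The SAP's test of the intervention is "a series of repeated-measures multivariate analysis of variance (MANOVAs) were used with time (baseline, post-intervention, and follow-up) as the within-subjects factor". The only other factor in the model is arm, entered between subjects; no class, lecturer or sport term is listed. The only remark on false positives is that "MANOVA is likely to prevent type I error when dependent outcomes may be correlated". The follow-up step is "Post hoc Scheffe analyses were conducted to determine contributing factors to significant MANOVA F values". One-way ANOVAs "were used to assess differences between groups in the baseline measures of demographic information, each outcome measure" and of the lesson-observation percentages.

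Neither document mentions a mixed model, GEE, cluster-robust standard errors, a class-level summary, an ICC or a design effect.

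**The concern.** The unit randomised is the class and the unit analysed is the student. Students in one class share a teacher, a timetable, classmates and ten lessons, so their changes may be correlated. A model with only time and group treats about 341 students as 341 independent pieces of evidence, when the randomisation supplied 16.

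The SAP's remark on type I error does not meet this. MANOVA allows for correlation between outcomes within a student, not between classmates. The Scheffe tests, as described, add no class term either.

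Group-by-time is the trial's test of the curriculum effect. If classes change in their own way, a significant result cannot be taken at face value.

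**Working it through.** **Inputs.** From the protocol: 8 classes per arm (required number), N = 341, effect size 0.25, alpha 0.05, power 0.95, dropout 10-20%, and 64 accelerometer students per arm. Assumed: 341 is the total, classes are of equal size, and the ICC of change is 0.01, 0.02, 0.05 or 0.10.

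**The plan's own figure.** A noncentral-F calculation for independent observations (f = 0.25, alpha 0.05, power 0.95) gives exactly 341 with 6 numerator degrees of freedom. The documents do not state those degrees of freedom, so this is only a match. It does show that 341 can be reached with no allowance for clustering.

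**Students per class (m).** Analysed: 341/16 = 21.3. Enrolled at 20% dropout: (341/0.8)/16 = 26.6. Accelerometry, if spread evenly: 128/16 = 8.

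**Class-specific change in both arms.**
- Design effect: DE = 1 + (m − 1) × ICC.
- True error of one change contrast: 2 × (1 − Φ(1.96/√DE)).
- True error of the multivariate test of one outcome over three time points (two change contrasts, class covariance proportional to student covariance): 0.05^(1/DE).

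Example, m = 21.3 and ICC 0.05: DE = 1 + 20.3 × 0.05 = 2.02, and the true SE is √2.02 = 1.42 times the naive SE. The errors are 16.7% and 22.6%.

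**Class-specific change in the sport education arm only.** DE is replaced by r = [ICC/8 + 2(1 − ICC)/(8m)] / [(2 − ICC)/(8m)].

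| True error of a nominal 5% test | ICC 0.01 | 0.02 | 0.05 | 0.10 |
|---|---|---|---|---|
| DE, m = 21.3 / 26.6 | 1.20 / 1.26 | 1.41 / 1.51 | 2.02 / 2.28 | 3.03 / 3.56 |
| One contrast, both arms | 7-8% | 10-11% | 17-19% | 26-30% |
| Multivariate, both arms | 8-9% | 12-14% | 23-27% | 37-43% |
| One contrast, one arm | 6-7% | 7-8% | 11-13% | 17-20% |
| Multivariate, one arm | 7% | 8-9% | 14-16% | 24-28% |
| Accelerometry (m = 8), one contrast | 6% | 7% | 9% | 13% |
| Accelerometry (m = 8), multivariate | 6% | 7% | 11% | 17% |

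Simulation with m = 21 agrees: 7.6/9.6/16.8/25.6% for one contrast and 8.5/12.0/22.5/36.8% for the multivariate test, against 4.7-4.8% at ICC 0. If a single class shift drives both changes, the multivariate test gives 7.0/10.0/16.4/25.2%.

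**What cancels.** Stable class differences leave group-by-time at about 5%. They do not cancel from the group main effect or the baseline ANOVAs. With class shares of 0.01/0.02/0.05/0.10 of total variance, the baseline ANOVA error is 7/9/17/26%.

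**Lecturer-shared change.** Let rc be the class-specific share of the variance of change and rl the lecturer or sport share. If each lecturer taught one class per arm, DE becomes m × rc + 1 − rc − rl. With rl = 0.05, the one-contrast error is 6.8-7.4%, 9.2-10.5%, 16-19% and 26-30% at rc = 0.01, 0.02, 0.05 and 0.10. If instead both of a lecturer's classes were in the same arm, lecturer-shared change alone gives 26% (share 0.05) or 39% (share 0.10).

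**Class-level analysis.** Under the same settings (ICC 0 to 0.10), a t-test on class means with 14 df holds 4.5-5.2%. The balanced-data mixed-model F with class-by-time error (2, 28 df) holds 4.5-5.4%.

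**The case against.** The strongest reply is that grouping by lecturer and sport before randomisation already protects the test. In part it does. If each lecturer taught in both arms, lecturer-shared change cancels from the contrast but stays in the MANOVA error term, so with no class-specific change the test is slightly conservative. Inflation needs (m − 1) × rc > rl. At rl = 0.05 that means rc above about 0.0025 (0.05/20.3) for 21 students per class, or 0.0020 (0.05/25.6) for 27. The protection is real but is lost at very small class-specific variance. The ordinary reading of the protocol is assignment within those groups, so the same-arm lecturer case is a contingency. Table 1 and the flow figure were missing from the text reviewed and may settle it.

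Other points qualify the size:
- A three-time-point MANOVA normally needs complete records. With 427 enrolled, 341 to 384 would remain, or 21 to 24 per class. At 24 and ICC 0.10 the errors are 28% and 40%, not 30% and 43%.
- A class shift that persists to follow-up gives the lower multivariate figures, 7-25%.
- All figures above are for one outcome. Testing three outcomes jointly, with rl = 0.05, gave 9-11% at rc = 0.01 and 38-47% at 0.05, so this point works against the plan.
- Fixed teams in the sport education arm, against teams changed each lesson in the control arm, suggest mainly team-level clustering. They are weak evidence for a shift of the whole class.

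None of this changes the direction or the remedy. An unknown ICC is a reason to estimate it, not to set it to zero.

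**Conclusion.** The concern holds and must be fixed. The mismatch between unit of randomisation and unit of analysis is certain from the text. The size is not, because it depends on an ICC of change that the documents do not give. Inflation is small at 0.01 (7-8% for one contrast) and serious from about 0.05 (17-19% for one contrast, 23-27% for the multivariate test). It is smaller if only the sport education arm is affected, and smaller for accelerometry. It vanishes if class-specific change is negligible beside lecturer-shared change that is balanced across arms. The figures assume 16 equal classes of 21 to 27 students.

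**What to change.** 1. State which lecturer taught which class in which arm, in the SAP or by reference to Table 1.
2. For each outcome, replace the student-level MANOVA with a linear mixed model. Fixed effects: group, time, group-by-time, and the grouping factors (sport type or, where lecturers taught in both arms, lecturer) with their time interactions. Random effects: student, class and class-by-time. Use Satterthwaite or Kenward-Roger degrees of freedom. The time interactions are needed because a grouping main effect alone leaves lecturer-shared change in the error term.
3. If the model cannot be fitted, do not drop the student or class intercepts. Compare the 16 class-mean changes between arms with 14 df, or paired by lecturer with 7 df only if each lecturer is confirmed to have taught one class per arm. If a lecturer's classes were all in one arm, treat lecturer as the top-level cluster (6 df with 4 lecturers per arm).
4. Compare baselines at class level or only descriptively, and report the ICC of change for each outcome.
5. Because separate models replace the joint test, say how multiplicity across outcomes is handled.

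**Cost.** SAP rewording and re-analysis of data already held, provided class identifiers were kept. Intervals will usually widen and p-values rise, although adjusting for lecturer or sport may recover precision. Going from 14 to 7 df raises the squared critical value by 22%: (2.365/2.145)² = 1.216. Pairing must therefore remove about 18% of the variance to break even (1 − 1/1.216).

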Physical activity measures The globally standardized and validated short version of the International Physical Activity Questionnaire was used to measure self-report physical activity levels (Craig et al. 2003; Hallal et al. 2012). Four generic items of vigorous, moderate, walking, and sitting were included to obtain the physical activity levels from the participants. Example item included the following: During the last 7 days, on how many days did you do vigorous physical activity like heavy lifting, digging, aerobics, or fast cycling (vigorous)? The total

duration of different intensities of physical activity which occurred for at least 10 uninterrupted minutes in the last 7 days was used for calculations (Booth 2000).

Accelerometers (Actigraph wGT3X+) were used to measure the objective physical activity levels (light, moderate, and vigorous) of participants, and physical activity intensity was calculated as a metabolic value (Evenson et al. 2008). The dynamic range of accelerometers is \pm 6MET with 3 axes and 3 mg/LSB of sensitivity. Only data that recorded more than 8 h per day and 5 days per week were used for analysis.

SOFIT is a validated and reliable momentary time sampling and interval observation instrument to gather quantitative data for assessing physical activity during PE lessons (McKenzie et al. 1992). SOFIT includes three intensities of students' physical activity levels (lying down, sitting, standing, walking, vigorous), lesson context (general, knowledge, fitness, skill practice, game play, free time), and teacher behavior (promotes fitness, demonstrates fitness, instructs generally, manages, observes, or other task) or teacher interactions (promoting "in-class" or "out-of-class" physical activity). Each category is coded using interval coding every 20 s (10 s observe; 10 s record) throughout the lesson. The observer decides on what is occurring at the moment an observation interval ends.

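### The planned MANOVA has no class term, missing-data method or analysis population; a class-aware mixed model on all observed waves is the better analysis, though its precision gain may be nil

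*SAP*

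**What the plan says.** The SAP (Statistical Analysis Plan) evaluates the intervention by a series of repeated-measures MANOVAs "with time (baseline, post-intervention, and follow-up) as the within-subjects factor" and group as the between-subjects factor, with interest in the interaction of the two. It justifies the choice partly by saying that "MANOVA is likely to prevent type I error when dependent outcomes may be correlated". It names no class or lecturer term, baseline covariate, analysis population or missing-data method.

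The protocol (Eligibility and randomization) describes a class-randomised design: "PE classes were initially grouped by lecturers and types of sports" before allocation. Loss is expected: "In anticipation of 10–20% of the dropout rate across data collection phases, this led to a required number of 8 classes for each" arm.

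Under Data collection protocol, a primary outcome is "self-reported and objective physical activity levels". The objective part comes from "a subsample of 64 randomly selected student participants per intervention group", measured at baseline, week 11 and week 15. The only data-inclusion rule is under Physical activity measures: "Only data that recorded more than 8 h per day and 5 days per week were used for analysis". That rule defines a usable recording. It does not say who is analysed or what happens to a student with one unusable wave.

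**The concern.** There are three linked problems.

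- **Class is ignored.** Classes were randomised, but the MANOVA treats students as independent. If class effects shift between waves, the variance of the change contrast is understated.
- **Partial records are probably discarded.** A repeated-measures MANOVA needs a complete set of values per student. By default, a student lacking any dependent variable at any wave is dropped, along with the values that were observed. The SAP does not write this rule down, nor any other.
- **Baseline is an outcome level.** The interaction compares changes from baseline. This is valid under randomisation but generally less efficient than adjusting for baseline.

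The second problem matters most for the accelerometer subsample. It is small, it carries part of a primary outcome, and the wear-time rule can remove a student at any of three waves. With no stated method or population, a reader cannot judge whether selective loss affected the result.

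**Working it through.** **The plan's own figure.** An F test with effect size f = 0.25, alpha 0.05, power 0.95 and 6 numerator df needs exactly 341 students. The 6 df are my inference; a two-group F test with 1 df needs 210. Neither calculation allows for clustering. I use 341 only for class size: 341/16 = 21.3 students per class. For accelerometers, 64/8 = 8 per class if the subsample is spread evenly (assumption).

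**Assumed inputs, not in the documents.** Within-student correlation rho 0.3-0.7; ICC 0.01-0.10; correlation of class effects between waves (pi) 0.5-1.0.

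**1. Baseline adjustment, known slope.** Without clustering, adjusted/change variance is (1 - rho²)/[2(1 - rho)] = (1 + rho)/2, which is 0.65, 0.75 and 0.85 for rho 0.3, 0.5 and 0.7. With class effects in both models it is (1 + r)/2, where r is the correlation of class means between waves:

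r = [m·ICC·pi + (1 - ICC)·rho] / [1 + (m - 1)·ICC]

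| m | ICC, pi, rho | r | (1 + r)/2 |
|---|---|---|---|
| 21.3 | 0.01, 0.5, 0.3 | (0.107 + 0.297)/1.203 = 0.335 | 0.668 |
| 21.3 | 0.10, 1.0, 0.7 | (2.131 + 0.630)/3.031 = 0.911 | 0.955 |
| 8 | 0.01, 0.5, 0.3 | (0.040 + 0.297)/1.070 = 0.315 | 0.657 |
| 8 | 0.10, 1.0, 0.7 | (0.800 + 0.630)/1.700 = 0.841 | 0.921 |

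**2. Slope estimated from 16 class means.** This costs about 1 + 1/12 = 1.083 in variance. Simulation (40,000 trials in each of 27 parameter cells) gives 0.715-1.025 for questionnaires and 0.711-1.001 for accelerometers, with type I error 4.7-5.2% on 13 df. On complete records the gain can therefore be nil in both datasets.

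**3. Lecturer as a fixed effect in both models.** If each of eight lecturers teaches one class per arm (assumption), simulation gives 0.80-1.14 (21 per class) and 0.78-1.10 (8 per class). A further cost of (t6/t7)² = 1.07 applies for degrees of freedom. The gain can become a loss.

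**4. Partial records.** At the documents' 10-20% dropout, complete students number 64 × 0.8 = 51.2 to 64 × 0.9 = 57.6, or 51-58 of 64. If half of the loss falls between weeks 11 and 15 (assumption), 64 × 0.05 = 3.2 to 64 × 0.10 = 6.4 per group have a week-11 record that listwise deletion would discard. For questionnaires under the same dropout pattern, using all waves rather than complete cases, with adjustment and class effects in both models, cuts variance by 1-12% post-intervention and at most 4% at follow-up. Wear-time loss would come on top for accelerometers, but no rate is given. At an assumed 80-90% valid per wave, with within-person correlation of validity 0.5, the saving is 4-16%.

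**5. Against what the MANOVA would print.** The true variance of the clustered change contrast divided by its nominal unclustered variance is [1 + (m - 1)·ICC](1 - r)/[1 - ICC·pi - (1 - ICC)·rho]. At ICC 0.10, pi 0.5, rho 0.7 this is 3.031 × 0.441/0.32 = 4.2 (21.3 per class) and 1.7 × 0.394/0.32 = 2.1 (8 per class). At pi = 1.0 it is 1.0. The correct SE of the adjusted contrast (known slope) relative to the nominal MANOVA SE is:

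sqrt{[1 + (m - 1)·ICC](1 - r²) / (2[1 - ICC·pi - (1 - ICC)·rho])}

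It runs from 0.84 to 1.80 (questionnaires) and from 0.82 to 1.30 (accelerometers).

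**The case against.** The strongest reply is that the change contrast is valid under randomisation, bias is not shown, and the efficiency argument rests on assumed correlations. Much of that stands. The tempting stronger readings fail:

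- **That the mixed model must be more precise, at least for accelerometers.** Steps 2 and 3 show otherwise, and an upper bound such as 0.95 fails once lecturer is a fixed effect. If rho were 0.9 with ICC 0.10 and pi 1.0, the known-slope ratios would be 0.985 and 0.974, and the slope cost would remove the gain.
- **That a third to a half of the subsample is lost.** At 80-90% validity independently at each wave, completers would be 64 × 0.8³ = 33 to 64 × 0.9³ = 47. Both the rates and the independence are assumptions at the extreme; the documents support only 51-58.
- **That the SAP prescribes complete-case analysis.** It is silent; deletion is the default of the method.
- **That baseline adjustment is always safer.** If students chose classes knowing the allocation, a stable baseline difference D may exist. A change contrast removes it; adjustment with slope b leaves (1 - b)·D. The documents do not say when students chose classes.
- **That any mixed model uses every wave.** Only one with baseline as an outcome does.

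The participant-flow figure was not available to me. Its caption covers enrolment and allocation, so it is unlikely to settle how missing waves are handled. None of this restores the class term or supplies the missing statements.

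**Conclusion.** The point holds as a weakness of the analysis that should be corrected, with medium confidence in the size of the benefit. The firm part comes from the text alone: randomised classes, no class term, expected dropout, and no stated population or missing-data method.

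The gain from baseline adjustment is conditional on the assumed correlations and runs from about a third of the variance to nothing, or below zero with fixed lecturer effects. Recovery of partial records should help most in the accelerometer subsample. The wear rule can remove single waves there, and with 8 students per class more of the variance lies between students. The documents do not allow that help to be sized. A reader might infer more power or a smaller printed SE; neither is claimed, and the correct SE may well be larger than the MANOVA's.

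**What to change.** - State the analysis population, with students analysed in the arm to which their class was randomised, and the missing-data method.
- For each outcome, fit a likelihood-based linear mixed model to all observed waves, with unstructured within-student covariance, a random class effect that may differ by wave (fixed class effects are confounded with arm) and small-sample degrees of freedom for 16 classes, such as Kenward-Roger. Report group contrasts at post-intervention and follow-up.
- Model baseline as an outcome with equal arm means only if students could not choose classes knowing the allocation. Otherwise enter class-mean baseline and the student's deviation from it as separate covariates, impute missing baselines, and report the change contrast alongside. Avoid one pooled slope: its variance reached 1.476 times that of the change contrast at 21 per class in simulation.
- Say how lecturer and sport type enter the model, for example lecturer as a random effect.
- Name a multiplicity rule, such as Holm, to replace the MANOVA omnibus step.
- Keep the complete-case MANOVA as a sensitivity analysis.

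No new data are needed. Both documents are written in the past tense, so this means a re-analysis as well as new wording, possibly in other software. The other costs are reliance on missing at random, few degrees of freedom, and an explicit multiplicity penalty per outcome.
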